10.2.3. Planned Interim Efficacy and Futility Analyses for the Phase 1 Randomization

Prior to trial completion, only the DSMB and a designated study statistician from the SDRC will have access to data with unblinded randomization assignments. During each interim look, the DSMB could recommend early trial termination due to efficacy or futility of the primary objective or any operational inadequacy as follows.

1. Efficacy: strong evidence is found for the primary hypothesis, indicating that a significant difference in changes in BPI Interference scores between PCST and Usual Care at Week 12 is likely to be concluded, resulting in a decision to stop the trial for superior efficacy.

2. Futility: weak evidence is found for the primary hypothesis, indicating a significant difference in changes in BPI Interference scores between PCST and Usual Care at Week 12 is unlikely to be concluded, resulting in a decision to stop for futility.
3. Operational inadequacy: failure to obtain success in the implementation of the trial such as slow recruitment, poor retention, improper data handling, or inability to implement the protocol.

For Phase 1 of the trial, one interim analysis is planned at 50% information time. However, the DSMB may request additional interim analyses and therefore a plan for an interim analysis with two looks at 50% and 75% information time is also provided. The 50% and 75% information times are defined as the times at which the randomized participants #320 and #480, respectively, have completed the Week 12 visit.

Interim Analysis with One Look at 50% Information Time. To accommodate the additional interim look, a spending-function approach⁶⁴ will be used to determine stopping bounds for efficacy and futility. For efficacy, an alpha-spending function is chosen to resemble the O'Brien-Fleming bounds.⁶⁵ For futility, a beta-spending function is chosen to select a bound that approximates a conditional power of 20% or below. Stopping boundaries are depicted in Table 10.3 for a power of 90% and a two-sided type 1 error of 5% for an interim analysis with one look at 50% information time. At the 50% information time, if the test statistic for the primary objective, i.e., regression coefficient β_4 divided by its standard error, is less than -2.89 (greater than -0.97), the trial will stop for efficacy (futility).

Table 10.3. Stopping Boundaries of Efficacy and Futility for a Power of 90% and at a Two-Sided Type 1 Error of 5% for an Interim Analysis with One Look at 50% Information Time

	Interim Analysis Look 1	Final Analysis
Information Time	50%	100%
Efficacy Boundary		
Test Statistic Critical Value	-2.89	-1.97
Conditional Power at the Boundary	99.9%	
Futility Boundary		
Test Statistic Critical Value	-0.97	-1.97
Conditional Power at the Boundary	20%	

gsDesign R package⁶⁶ used to calculate stopping boundary and conditional power

Interim Analysis with Two Looks at 50% and 75% Information Time. To accommodate a second interim look at 75% information time, stopping boundaries are depicted in Table 10.4 for a power of 90% and a two-sided type 1 error of 5% for an interim analysis with two looks at 50% and 75% information time. At the 50% information time, if the test statistic for the primary objective, i.e., regression coefficient β_4 divided by its standard error, is less than -2.89 (greater than -1.09), the trial will stop for efficacy (futility). At the 75% information time, if the test statistic is less than -2.50 (greater than -1.53), the trial will stop for efficacy (futility).

Table 10.4. Stopping Boundaries of Efficacy and Futility for a Power of 90% and at a Two-Sided Type 1 Error of 5% for an Interim Analysis with Two Looks at 50% and 75% Information Time

	Interim Analysis Look 1	Interim Analysis Look 2	Final Analysis
Information Time	50%	75%	100%
Efficacy Boundary			
Test Statistic Critical Value	-2.89	-2.50	-1.99
Conditional Power at the Boundary	99.9%	96.3%	
Futility Boundary			
Test Statistic Critical Value	-1.09	-1.53	-1.99
Conditional Power at the Boundary	20%	32%	

If the interim analysis with two looks at 50% and 75% information time is conducted, the minimum detectable differences depicted in Table 10.2 will be updated by replacing the inflation factor of 1.173 for the interim analysis with one look at 50% information time with the inflation factor of 1.277 for the interim analysis with two looks at 50% and 75% information time. Table 10.5 depicts the minimum detectable difference between the PCST and Usual Care groups in change in BPI Interference from baseline to 12 weeks, for a power of 90%, at a type 1 error of 5%, an attrition rate of 20%, standard deviations of change of 2 and 3, a total number of participants ranging from 480 – 800 (participant numbers per Clinical Center ranging from 60 to 100), intra-class correlation coefficients of 0 and 0.02, and an interim analysis of two looks at 50% and 75% information time.

Table 10.5. Minimum Detectable Differences between the PCST and Usual Care Groups in the Change from Baseline to Week 12 in the BPI Interference

Row	Total N	Clinical Center n	ICC	Minimum Detectable Between-Group Difference in Change in BPI Score ¹	
				If SD = 2	If SD = 3
1	800	100	0	0.58	0.87
2	640	80	0	0.65	0.97
3	480	60	0	0.75	1.13
4	800	100	0.02	0.76	1.14
5	640	80	0.02	0.82	1.22
6	480	60	0.02	0.90	1.35

¹Effect sizes determined for power of 90%, type 1 error of 5%, attrition rate of 20%, standard deviations of change of 2 and 3, and interim analysis of two looks at 50% and 75% information time, using two-sample t tests.

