10.2.2.1. Analyses of the Primary Endpoint for the Phase 1 Randomization

Question 1 (Table 10.1): Does a PCST intervention consisting of weekly, live, coach-led sessions improve outcomes at 12 weeks?

Question 1 addresses the primary trial hypothesis. The primary efficacy endpoint, the change in BPI Interference between baseline and 12 weeks, and will be analyzed using a linear mixed effects model.⁶² The linear mixed effects model will include fixed effects of intervention, time, and interactions between intervention and time, taking into account the repeated measures over time and clustering of recruitment sites via random effects. All repeated measures of the BPI Interference scores at baseline and 12 weeks will be included in the model as the dependent variable. The linear mixed effects model is expressed as

$$y_{ijk} = \beta_0 + \beta_1 X_{ij} + \beta_2 I(T_{ijk} = 12) + \beta_3 X_{ij} I(T_{ijk} = 12) + \gamma^T \mathbf{W}_{ij} + \theta_i + \alpha_{ij} + \varepsilon_{ijk},$$

where y_{ijk} is the BPI Interference score for participant ij ($i = 1, 2, \dots, 14$; $j = 1, 2, \dots, n_i$; n_i is number of participants from recruitment site i) at time point k ($k = 1, 2$), X_{ij} is the binary intervention indicator ($X_{ij} = 1$ if PCST; $X_{ij} = 0$ if Usual Care) for participant ij , T_{ijk} is the study weeks for participant ij at time point k ($T_{ij1} = 0$ and $T_{ij2} = 12$), $I(\cdot)$ is an indicator function returning 1 (0) if the event is true (false), \mathbf{W}_{ij} is a vector of baseline measures, including the stratification factors, for participant ij , β 's and γ are regression parameters for the fixed effects, θ_i and α_{ij} are the regression parameters for the random effects for recruitment site i and participant ij , respectively, and ε_{ijk} is the random error for participant ij at time point k . Model diagnostics will be conducted to examine the assumption of normality. If there are potential violation of the assumptions, transformations of the data beginning with a log transformation will be explored. The primary efficacy estimand is the contrast of PCST and Usual Care for the change at the 12-week time point; i.e., β_3 . Differences in changes, their 95% confidence intervals, and p-values will be presented.

Question 2 (Table 10.1): Does a PCST intervention consisting of weekly, live, coach-led sessions for 12 weeks followed by IVR for 12 weeks improve outcomes at 24 weeks?

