To answer this question, the aforementioned linear mixed effects model is revised by adding the BPI Interference score at 24 weeks to the dependent variable. The linear mixed effects model is expressed as

$$y_{ijk} = \beta'_0 + \beta'_1 X_{ij} + \beta'_2 I(T_{ijk} = 12) + \beta'_3 I(T_{ijk} = 24) + \beta'_4 X_{ij} I(T_{ijk} = 12) + \beta'_5 X_{ij} I(T_{ijk} = 24) + \gamma'^T \mathbf{W}_{ij} + \theta'_i + \alpha'_{ij} + \varepsilon'_{ijk},$$

where y_{ijk} is the BPI Interference score for participant ij at time point k ($k = 1, 2, 3$) and $T_{ij3} = 24$. The estimand for **Question 2 in Table 10.1** is the contrast of PCST and Usual Care for the change at the 24-week time point; i.e., β'_5 . Differences in changes, their 95% confidence intervals, and p-values will be presented.

Question 3 (Table 10.1): Are the effects of PCST sustained?

To answer this question, the aforementioned linear mixed effects model is revised by adding the BPI Interference score at 36 weeks to the dependent variable. The linear mixed effects model is expressed as

$$y_{ijk} = \beta_0'' + \beta_1'' X_{ij} + \beta_2'' I(T_{ijk} = 12) + \beta_3'' I(T_{ijk} = 24) + \beta_4'' I(T_{ijk} = 36) + \beta_5'' X_{ij} I(T_{ijk} = 12) + \beta_6'' X_{ij} I(T_{ijk} = 24) + \beta_7'' X_{ij} I(T_{ijk} = 36) + \gamma''^T W_{ij} + \eta'' V_{ij} I(T_{ijk} \geq 24) + \delta'' Z_{ij} I(T_{ijk} \geq 24) + \theta_i'' + \alpha_{ij}'' + \varepsilon_{ijk}''$$

where y_{ijk} is the BPI Interference score for participant ij at time point k ($k = 1, 2, 3, 4$), $T_{ij4} = 36$, V_{ij} is the binary buprenorphine eligibility indicator ($V_{ij} = 1$ if buprenorphine eligible; $V_{ij} = 0$ if not buprenorphine eligible), Z_{ij} is the binary buprenorphine indicator ($Z_{ij} = 1$ if initiated buprenorphine; $Z_{ij} = 0$ if declined buprenorphine), and η'' and δ'' are regression parameters for the fixed effects. The estimand for **Question 3** in **Table 10.1** is the contrast of PCST and Usual Care for the change at the 36-week time point; i.e., β_7'' . Differences in changes, their 95% confidence intervals, and p-values will be presented.

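### Both interim stopping rules name a coefficient, β_4, that does not exist in the primary model, whose estimand is β_3

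*Combined protocol and SAP*

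**What the plan says.** Section 10.2.2.1 (Question 1) sets out the primary model. Its β terms are an intercept β_0, intervention β_1, Week 12 β_2, and intervention by Week 12 β_3, followed by baseline covariates and random effects for site and participant. It is a two-visit model: "All repeated measures of the BPI Interference scores at baseline and 12 weeks will be included in the model as the dependent variable". The target is explicit: "The primary efficacy estimand is the contrast of PCST and Usual Care for the change at the 12-week time point; i.e., β_3".

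Section 10.2.3 gives the one-look stopping rule. The test statistic for the primary objective is "regression coefficient β_4 divided by its standard error, is less than -2.89 (greater than -0.97", the first value being the efficacy bound and the second the futility bound. The two-look rule uses the same symbol: "regression coefficient β_4 divided by its standard error, is less than -2.89 (greater than -1.09".

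No equation in the statistical section contains an unprimed β_4. The Question 2 and Question 3 models write their coefficients with single and double primes, and the Phase 2 model in Section 10.3.3 stops at β_1. Neither the statistical section nor the amendment history reconciles the labels.

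**The concern.** This sentence is the operative rule that the designated unblinded statistician would program for the DSMB. Taken literally, it cannot be computed from the primary model. Someone looking for a fourth coefficient that is a Week 12 treatment contrast will find one in the Question 2 model: β'_4, estimated with Week 24 scores added. The interim statistic would then come from a three-visit model and the final primary test from a two-visit model. The group sequential calculation treats the two as successive values of one statistic. The DSMB charter (Section 14.3) also asks for stopping rules that the protocol defines clearly, and model choice should not be left open at an unblinded look.

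**Working it through.** **1. Are the boundary values themselves sound?**

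Inputs from Section 10.2.3: two-sided alpha 5% (0.025 per side), power 90%, a look at 50% information, and a spending function resembling O'Brien-Fleming. The spending parameter is not stated. Hwang-Shih-DeCani spending with γ = -4 and γ = -5 was tried, with non-binding futility.

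- Alpha spent at the 50% look with γ = -5: 0.025 × (1 − e^2.5)/(1 − e^5) = 0.0019, giving a critical value of -2.895 and a final value of -1.972. Table 10.3 states -2.89 and -1.97. With γ = -4 the first value is -2.75, which does not match.
- Two looks, γ = -5: -2.895, -2.500 and -1.993. Table 10.4 states -2.89, -2.50 and -1.99.
- One-look conditional power under the current trend is Φ{(z/√0.5 − 1.97)/√0.5}, with z the absolute value of the bound. For 0.97: (1.372 − 1.97)/0.707 = −0.846, giving 19.9% (stated 20%). For 2.89: (4.087 − 1.97)/0.707 = 2.994, giving 99.9% (stated 99.9%).
- Inflation factor: (3.508/3.2415)² = 1.171 (stated 1.173).
- Sample size per arm: 320/1.574 × 0.8/1.173 = 138.7 (stated about 139).

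The two-look futility bounds were not re-derived. None of these calculations uses a model coefficient, so correcting the label leaves them all unchanged.

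**2. Which coefficient fits the description?**

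| Source | Term | Meaning |
|---|---|---|
| Question 1 model (baseline, Week 12) | β_3 | PCST versus Usual Care, change to Week 12; named primary estimand |
| Section 10.2.3, both rules | β_4 | in no equation |
| Question 2 model (baseline, Weeks 12 and 24) | β'_4 | PCST versus Usual Care, change to Week 12, from a secondary model |

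Section 10.2.3 defines efficacy and futility by the Week 12 between-group difference in change. Within the primary model only β_3 answers to that.

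**3. What if β'_4 were used at the 50% look?**

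Assumptions: 320/2 × 0.8 = 128 analysed per arm, SD of change 2, true differences 0, 0.30 and 0.62. Half of participants with Week 24 data and between-visit correlations of 0.5 and 0.4 are also assumed; neither is in the documents. Random-intercept models were fitted to 1,500 simulated interim data sets per effect size. A second run used 500 per effect size without a site effect.

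- The SD of the difference between the two Z statistics was 0.04 to 0.08 (0.03 to 0.08 in the second run).
- The futility decision changed in about 1% of looks, and the efficacy decision in up to about 3%, the latter at the detectable difference of 0.62.
- In the second run the estimated effect was the same in both models; only the standard error moved, by about 2% on average. With all correlations at 0.5 the standard-error ratio averaged 1.00.

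A hand check agrees in size. The standard error is 2 × √(2/128) = 0.25, so a true difference of 0.62 gives an expected |Z| of 2.48. A 2% change in standard error shifts Z near 2.89 by about 0.058. Multiplying by the normal density at 2.89 − 2.48 = 0.41, which is 0.367, gives about 2% of looks changed. At the futility bound the shift is 0.02 × 0.97 = 0.019, and with a density of at most 0.399 that is under 1%.

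**The case against.** The strongest reply is that this is a slip of notation that no competent statistician would act on. The sentence itself says that the statistic is for the primary objective. Sections 10.1, 10.2.1 and 10.2.2.1 all define that objective as the Week 12 difference in change, and only β_3 fits. That stands, and it limits the weight of the point.

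A lost prime in the text as extracted from the PDF also cannot be excluded. It would not remove the problem, because β'_4 is still not the named estimand, but it would place the issue in the nearly harmless case above. The DSMB recommends and NIDDK decides, so the symbol alone does not stop the trial. That helps only in part, since the rule says that the trial will stop.

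A reader might infer something worse: that the decision rests on a wrong quantity, for instance the fourth coefficient of the Question 3 model, which is a Week 36 time effect with no treatment comparison. The documents do not support this. That coefficient carries a double prime, belongs to a secondary model with buprenorphine terms, and cannot be described as a PCST versus Usual Care contrast at Week 12. A reader might also infer that the boundaries are invalid because they were derived for another model. They follow from information time, alpha, power and the spending functions, not from any regression model.

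**Conclusion.** The error is real and small. Both stopping rules name a coefficient that the primary model does not contain, and nothing in the documents reconciles this. β_4 is best described as an undefined label. The intended contrast can be inferred, and the boundary figures re-derived here hold.

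The one plausible misreading, β'_4 of the Question 2 model, tests the same contrast from a different model and would change about 1% of futility and up to 3% of efficacy decisions. These percentages depend on the assumed correlations and Week 24 availability, and the standard-error shift averages out to nothing when all correlations are equal at 0.5. The conclusion does not need them: it rests on the contradiction between Sections 10.2.2.1 and 10.2.3, which deserves correction because it sits in a decision rule.

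**What to change.** In Section 10.2.3, in both the one-look and the two-look paragraphs, replace β_4 with β_3 of the Question 1 model in Section 10.2.2.1 (baseline and Week 12 scores). Add one sentence stating that the interim and final primary tests use that same model. The cost is one symbol in two paragraphs and one added sentence. Tables 10.2 to 10.5, the inflation factors and the sample size stay as they are.

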10.3. Statistical Considerations for the Phase 2 Intervention

This section describes statistical considerations for the exploratory objective of evaluating acceptability, tolerability, and efficacy of buprenorphine in Phase 2 of the trial. Participants who, at Week 24, meet the buprenorphine eligibility criteria are included in the following exploratory analyses.

Due to the exploratory nature of Phase 2, potential numbers of participants initiating buprenorphine and declining buprenorphine are illustrated in **Table 10.6 – Table 10.8** ranging from 20 per group to 80 per group.

Although we cannot predict how many participants among the 300 patients using opioids at trial enrollment will be eligible for the Phase 2 intervention at 24 weeks, under plausible assumptions we estimate that there will be at least 40 who are on sufficiently high doses of opioids at 24 weeks to meet the eligibility criteria for the buprenorphine intervention.

10.3.1. Acceptability

Participants who meet buprenorphine eligibility criteria at 24 weeks will be encouraged to switch from their full agonist opioid to buprenorphine. The acceptability objective explores the percentage of participants who initiate buprenorphine (acceptability), and also examines reasons for non-willingness to initiate buprenorphine (non-acceptability) (**Table 10.1; Question 4**). Table 10.6 depicts 95% confidence intervals for percentages of participants who initiate a switch from a full agonist opioid to buprenorphine for a range of numbers of participants eligible for and offered buprenorphine, and a range of percentages of participants who initiate a switch to buprenorphine.

Table 10.6. 95% Confidence Intervals for % of Participants Willing to Switch from a Full Agonist Opioid to Buprenorphine

Offered Buprenorphine, N	Initiated Buprenorphine, N	Initiated Buprenorphine, %	95% Confidence Interval for Initiated Buprenorphine, %
20	5	25	(8.7, 49.1)
40	10	25	(12.7, 41.2)
60	15	25	(14.7, 37.9)
80	20	25	(16, 35.9)
20	10	50	(27.2, 72.8)
40	20	50	(33.8, 66.2)
60	30	50	(36.8, 63.2)
80	40	50	(38.6, 61.4)
20	15	75	(50.9, 91.3)
40	30	75	(58.8, 87.3)
60	45	75	(62.1, 85.3)
80	60	75	(64.1, 84)

10.3.2. Tolerability

Among the participants who are offered and agree to switch to buprenorphine, the tolerability outcome provides the number (percentage) of participants who do not discontinue buprenorphine due to adverse effects (**Table 10.1; Question 5**). For those who discontinue buprenorphine due to adverse effects, reasons for non-tolerability will be examined. **Table 10.7** depicts 95% confidence intervals for percentages of participants who continue buprenorphine until the end of the study for a range of numbers of participants willing to switch from a full agonist opioid to buprenorphine and a percentage of participants who continue of 60%.

Table 10.7. 95% Confidence Intervals for % of Participants who Continue Buprenorphine Until the End of the Study (Week 36)

Offered Buprenorphine, N	Initiated Buprenorphine, N	Continued Buprenorphine until Week 36, N	Continued Buprenorphine until Week 36, %	95% Confidence Interval for Continued Buprenorphine until Week 36, %
20	5	3	60	(14.7, 94.7)
40	10	6	60	(26.2, 87.8)
60	15	9	60	(32.3, 83.7)
80	20	12	60	(36.1, 80.9)
20	10	6	60	(26.2, 87.8)
40	20	12	60	(36.1, 80.9)
60	30	18	60	(40.6, 77.3)
80	40	24	60	(43.3, 75.1)
20	15	9	60	(32.3, 83.7)
40	30	18	60	(40.6, 77.3)
60	45	27	60	(44.3, 74.3)
80	60	36	60	(46.5, 72.4)

¹Assumes a standard deviation of change of 2 and an attrition rate of 20%.

10.4. Safety Analyses

Proportions of participants with at least one adverse event and rates of adverse events will be determined. Differences between the PCST and Usual Care groups in the proportions and the rates will be compared using logistic regression models and Poisson regression models, respectively, adjusting for baseline measures. For participants who switch to buprenorphine, adverse events occurring during the buprenorphine phase (Weeks 24-36) will also be summarized.

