2.3. Risk / Benefit Assessment for the HOPE Trial Interventions

2.3.1. Known Potential Risks of Trial Interventions

The PCST intervention may increase distress for participants if sensitive topics are raised during the telehealth or IVR sessions. All prescribing decisions for participants will be made by the treating physicians rather than by the research team. Participants in both the PCST and Usual Care groups may have adverse effects from the non-opioid pain medications that are prescribed by treating (non-study) clinicians during the course of the study. Patients may experience withdrawal symptoms and other temporary discomfort due to reducing opioid doses, switching from one opioid medication to another, or transitioning to non-opioid medications. Because opioids may reduce the symptoms of restless leg syndrome in hemodialysis patients, reducing or discontinuing opioids may worsen this condition. Intervention clinicians will educate participants about withdrawal symptoms, take precautions to prevent withdrawal, and manage symptoms if they occur.

Common adverse effects of buprenorphine, the Phase 2 intervention, are similar to those of other opioids and include dizziness, headache, sedation, dry mouth, mouth numbness, constipation, insomnia, abdominal pain, drowsiness, fatigue, and numbness or tingling. An FDA report issued on January 12, 2022 identified dental issues such as tooth decay, cavities, oral infections, and loss of teeth, as newly recognized possible adverse effects of buprenorphine delivered via buccal or sublingual approaches. The FDA advises that these dental problems have been reported even in patients with no history of dental issues. The risk of these dental problems can be reduced by rinsing the mouth with water after using the drug, waiting at least an hour before teeth brushing, visiting a dentist shortly after starting buprenorphine, and having regular dental checkups. The FDA maintains that despite these risks, the benefits of buprenorphine medicines clearly outweigh the risks. As for all opioids, additive or synergistic interactions can occur between buprenorphine and central nervous system depressants including benzodiazepines and alcohol. Active, untreated substance use disorder is an exclusion criterion for the trial. Study investigators will educate participants eligible for the buprenorphine intervention about withdrawal symptoms, take precautions to prevent withdrawal, and manage symptoms if they occur.

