4.2.2.3. Secondary Outcomes: Clinical Events

The trial interventions are hypothesized to reduce the frequency of several clinical events that will be treated as secondary outcomes.

- Falls
- Hospitalizations
- Deaths

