6.1. Pain Coping Skills Training Intervention (PCST)

The PCST intervention will focus primarily on reducing pain interference in daily activities as well as other factors associated with pain, such as negative emotions and sleep disturbance, and will incorporate a strong emphasis on improving pain self-management skills. For participants who have recent or current opioid use, the PCST intervention will include motivational interviewing aimed at reducing opioid use. For participants who do not have recent or current opioid use, motivational interviewing skills will be focused on any identified adherence goals or a value-based skill that the participant is interested in acquiring. Although many components of PCST will be delivered in a structured manner, the approach will allow flexibility to adjust to a participant's personal circumstances.

The PCST training will be delivered by coaches using telehealth during Weeks 1 - 12 and Interactive Voice Response (IVR) during Weeks 13 - 24. The telehealth component will consist of weekly sessions, each lasting 45-50 minutes. The IVR content, intended to serve as booster sessions, will be delivered with daily telephone

interactions, each lasting 5 minutes. Both components of the intervention will be available in English and Spanish.

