9.2. Adverse Events of Interest

The following adverse events are anticipated in patients with chronic pain, opioid use, or treatment with the trial interventions, and will be considered AEs of Interest.

- Development of suicidality – based on response to question 9 of the PHQ-9
- Development of opioid use disorder or other substance use disorder
- Adverse effect from a medication started during the trial (including buprenorphine) to treat pain, opioid dependence, depression, or anxiety
- Falls
- Withdrawal symptoms
- Dental events in participants who have switched to buprenorphine

AEs of Interest will be ascertained during the contacts between the research coordinator and the participant that occur every 4 weeks through specific questioning and, as appropriate, by review of medical records. Information about the events will be recorded on the Adverse Event of Interest case report form (CRF) and entered into the data management system.

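### Section 10.4 prespecifies only an any-AE proportion and an overall AE rate for PCST versus Usual Care, so withdrawal symptoms, suicidality, substance use disorder and medication adverse effects have no planned between-arm analysis

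*Combined protocol and SAP*

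**What the plan says.** Section 10.4 sets out two summary measures: "Proportions of participants with at least one adverse event and rates of adverse events will be determined". It continues: "Differences between the PCST and Usual Care groups in the proportions and the rates will be compared using logistic regression models and Poisson regression models", with adjustment for baseline measures. It names no event type and makes no split by seriousness. Its last sentence adds a Weeks 24-36 summary for participants who switch to buprenorphine, which is not a randomized comparison.

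The events collected are more specific. Section 9.2 lists six kinds as "anticipated in patients with chronic pain, opioid use, or treatment with the trial interventions, and will be considered AEs of Interest": suicidality, opioid or other substance use disorder (OUD/SUD), adverse effects of certain newly started medications, falls, withdrawal symptoms, and "Dental events in participants who have switched to buprenorphine". Sections 7.4.2 and 7.5.2 have coordinators ask about AEs of Interest and SAEs every four weeks. By the definition in Section 9.1.2, hospital stays and deaths are SAEs.

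On direction of effect, Section 2.3.1 warns: "Patients may experience withdrawal symptoms and other temporary discomfort due to reducing opioid doses". Section 6.1 says that for participants with recent or current opioid use "the PCST intervention will include motivational interviewing aimed at reducing opioid use". Section 4.2.2.3, on falls, hospitalizations and deaths, says: "The trial interventions are hypothesized to reduce the frequency of several clinical events that will be treated as secondary outcomes".

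**The concern.** The protocol identifies particular harms and asks about them throughout follow-up, but the analysis plan commits to no between-arm estimate for four of the six. The two contrasts it does commit to are composites whose components may move in different directions. Withdrawal symptoms could rise under PCST, falls and hospitalizations are hoped to decline, and the dialysis SAEs listed in Section 9.3 are expected in both arms.

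The practical risk is in the final report. A statement that adverse events did not differ between arms could be true of the composite and still say little about withdrawal symptoms or suicidality. With no by-type analysis fixed in advance, the choice of which harms to show separately is left until the results are known.

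**Working it through.** **Coverage of each event type.** Section 10.4 gives no figure to reproduce, so the first check is which events have a PCST versus Usual Care analysis of their own anywhere in the plan.

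| Event | Own between-arm analysis? |
|---|---|
| Falls | Yes: count and time-to-first models, Section 10.2.3.2 |
| Hospitalizations | Yes: same section |
| Deaths | Yes: Cox model, same section |
| Withdrawal symptoms | None |
| Suicidality | None (the PHQ-9 is analysed as a depression outcome) |
| OUD/SUD | None |
| Medication adverse effects | None |
| Dental events | Arise by definition only in switchers |
| SAEs as a class | None |

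**Inputs for the size of the dilution.** From the documents: 640 participants, taken as 320 per arm; 20% attrition (Section 10.2.1), giving 320 × 0.8 = 256; falls in 25-30% of hemodialysis patients per year (Section 2.2.1). Assumed, because the documents give no AE rates: withdrawal symptoms in 5% of Usual Care and in 12% or 10% of PCST participants; background events in 40%, 60% or 70%; independence of event types within a participant.

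**Formula.** Two-sided 5% normal approximation for two proportions: power = Φ[(d − 1.96·se0)/se1] + Φ[(−d − 1.96·se0)/se1]. Here d is the difference, se0 uses the pooled proportion and se1 the separate proportions.

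*Withdrawal symptoms alone, 5% versus 12%, 320 per arm.* The pooled proportion is 0.085, so se0 = √(2 × 0.085 × 0.915/320) = 0.0220 and se1 = √((0.0475 + 0.1056)/320) = 0.0219. Then (0.07 − 1.96 × 0.0220)/0.0219 ≈ 1.22, and power is about 89%. With 256 per arm it is about 81%. For 5% versus 10% the figures are about 67% and 57%.

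*As part of any-AE.* The proportion with any event is 1 − (1 − b)(1 − w), where b is background and w is withdrawal. For b = 0.40 this gives 1 − 0.60 × 0.95 = 43.0% versus 1 − 0.60 × 0.88 = 47.2%.

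| Background | Difference, 5% vs 12% | Power | Difference, 5% vs 10% | Power |
|---|---|---|---|---|
| none (alone) | 7.0 points | 89% | 5.0 points | 67% |
| 40% | 4.2 | 19% | 3.0 | 12% |
| 60% | 2.8 | 11% | 2.0 | 8% |
| 70% | 2.1 | 9% | 1.5 | 7% |

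*Offset by fewer falls.* At a constant hazard, 25-30% per year becomes 1 − 0.75^(36/52) = 18% to 1 − 0.70^(36/52) = 22% over 36 weeks, so 20% is a reasonable base. Suppose that falls sit inside the background and drop from 20% to 15% under PCST. For a 40% background, 0.60 = 0.80 × 0.75, so the other events leave 75% event-free. Any-AE is then 1 − 0.80 × 0.75 × 0.95 = 43.0% in Usual Care and 1 − 0.85 × 0.75 × 0.88 = 43.9% in PCST. Across the three backgrounds the difference is 0.9, 0.6 and 0.5 points, and power is 5-6%. With 10% withdrawal the differences are −0.4, −0.25 and −0.2 points.

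*Rates.* For Poisson counts with 320 per arm, power ≈ Φ[|ln RR|/√(1/(320λ0) + 1/(320λ1)) − 1.96]. With λ of 0.05 versus 0.10 alone this is Φ(0.693/0.306 − 1.96), about 62%. Adding 0.5 other events per participant gives RR = 0.60/0.55 = 1.09 and power 13%. Adding 1.5 gives RR = 1.60/1.55 = 1.03 and power 7%.

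**The case against.** A reader might infer that the plan obliges the trial to report one pooled odds ratio and one pooled rate ratio and nothing else. The text does not support that. Section 10.4 is short and silent on event type, and it bars no by-type table. Section 4.1 says that safety is assessed through specific AEs of interest and SAEs, which suggests that type-level data will be available. What stands is narrower: by-type comparison is not prespecified.

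A reader might also infer that a rise in a named harm would go unseen. That is too strong. The Safety Committee reviews SAEs and AEs of Interest monthly (Section 11.5.2), and the DSMB sees AE data by masked group and may unmask (Section 14.3). If fewer falls offset more withdrawal symptoms, the separate falls model could show the fall reduction. But monitoring is not a prespecified final comparison, and a falls result does not estimate withdrawal symptoms.

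The numbers are open to challenge too. Every rate except background falls is assumed. If all withdrawal cases arose among 150 opioid users per arm (half of the guaranteed 300), 5% versus 12% overall would mean 16/150 = 11% versus 38.4/150 = 26% in that group, a large effect. The negative differences above are at most 0.4 points. They amount to no difference, so a claim that pooling reverses the result is not supported.

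Finally, Section 10.2.2 promises multiplicity control. Bonferroni over six event types (0.05/6) would cut power at 320 per arm to about 71% for 5% versus 12% and 41% for 5% versus 10%. So by-type analysis should be presented as estimation, without a promise of high power for each type.

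**Conclusion.** The point holds as a gap in prespecification. Four named AEs of Interest and SAEs as a class have no planned PCST versus Usual Care analysis, and the two contrasts that are planned mix possible harms with expected benefits and background dialysis morbidity. A flat any-AE result would therefore not be evidence that withdrawal symptoms, suicidality, OUD/SUD or medication adverse effects did not increase.

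The direction of the dilution follows from adding events unrelated to treatment. Its size rests on assumed rates, independence and 1:1 allocation; over the range shown, power drops from 67-89% to 7-19%. The primary efficacy result is unaffected, and no clinical rule is in question.

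**What to change.** In Section 10.4:

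- Report by arm the number and proportion of participants, the event rate, and the between-arm difference with 95% CI, separately for suicidality, OUD/SUD, medication adverse effects and withdrawal symptoms, and for SAEs as a class.
- Show withdrawal symptoms also within the opioid-use randomization stratum, where the risk mainly lies.
- Cross-refer falls, hospitalizations and deaths to their models in Section 10.2.3.2.
- Summarise dental events in buprenorphine switchers only, outside the randomized comparison.
- Keep any-AE as a descriptive summary.
- State that the by-type safety intervals are estimates without multiplicity adjustment, so that they do not conflict with Section 10.2.2.

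The cost is some SAP wording and a few more tables. No new data collection should be needed, provided that the single AE of Interest form described in Section 9.2 records event type; the documents do not show its layout. The drawback is several safety intervals in place of one, some of them wide.
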